### **12.4.2 Statistical model, hypothesis, and method of analysis**

The primary analysis of primary efficacy variable 1 to address the primary objective will be based on the following estimand:

- Population: Defined through appropriate inclusion/exclusion criteria to reflect the targeted population
- Variable: Percent change from baseline in LDL-C [The primary analysis time point is at Day 330.]
- Treatment: "Inclisiran first" implementation strategy or usual care
- Remaining intercurrent events: 1. Potential use of inclisiran by participants in the usual care group. This intercurrent event will be ignored in the analysis, as the design of the trial allows for participants in the usual care group to potentially use inclisiran. 2. Discontinuation of study treatment. This intercurrent event will be ignored in the analysis.
- Summary measure: Least-squares mean difference between "inclisiran first" implementation strategy and usual care

The null hypothesis is that the mean percent change from baseline in LDL-C at Day 330 for "inclisiran first" implementation strategy and usual care groups are equal. The alternative hypothesis is that the mean percent change from baseline in LDL-C at Day 330 for "inclisiran first" implementation strategy group is not equal to that of the usual care group.

Primary efficacy variable 1 will be analyzed using mixed-effects model repeated measures (MMRM) with treatment, visit, baseline, [REDACTED], treatment-by-visit interaction, and baseline-by-visit interaction as explanatory variables. An unstructured working correlation matrix will be assumed for this model (Diggle et al 2002). Least-squares mean of each treatment group, least-squares mean treatment difference, two-sided 97.5% confidence interval for the treatment difference, and p-value based on the fitted MMRM will be reported for each applicable visit (day). If the p-value based on a two-sided test for treatment effect at Day 330 is  $< 0.025$  and the corresponding least squares mean treatment difference ("inclisiran first" implementation strategy – usual care) is less than 0, statistical significance in favor of "inclisiran first" implementation strategy is shown. All efforts will be made to follow up participants until the end of the study. Participants will be expected to follow the visit schedule and assessments even after discontinuation of study treatment. Data after participants discontinued study treatment will be used in the analysis ("retrieved dropout").

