The primary analysis of primary efficacy variable 2 to address the primary objective will be based on the following estimand:

- Population: Defined through appropriate inclusion/exclusion criteria to reflect the targeted population and if a participant was not statin intolerant at the beginning of the trial
- Variable: Discontinuation of statin therapy (yes, no) [The primary analysis time point is at Day 330.]
- Treatment: "Inclisiran first" implementation strategy or usual care
- Remaining intercurrent events: 1. Potential use of inclisiran by participants in the usual care group. This intercurrent event will be ignored in the analysis, as the design of the trial allows for participants in the usual care group to potentially use inclisiran. 2. Discontinuation of study treatment. This intercurrent event will be ignored in the analysis.
- Summary measure: Treatment difference ("inclisiran first" implementation strategy – usual care) in the proportion of participants who discontinue statin therapy

The null hypothesis is that the difference ("inclisiran first" implementation strategy – usual care) in the proportion of participants who discontinue statin therapy at Day 330 is at least 0.15 (non-inferiority margin). The alternative hypothesis is that the difference ("inclisiran first" implementation strategy – usual care) in the proportion of participants who discontinue statin therapy at Day 330 is less than 0.15.

For primary efficacy variable 2, a one-sided 98.75% confidence interval for treatment difference ("inclisiran first" implementation strategy – usual care) in the proportion of participants who discontinued statin therapy at Day 330 will be computed using the normal approximation to the binomial distribution. Non-inferiority of the "inclisiran first" implementation strategy to usual care will be declared if the upper limit of the confidence interval does not exceed the non-inferiority margin of 0.15.

The primary analysis of both primary efficacy variables will be based on the Full Analysis Set.

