## 12.8 Sample size calculation

### 12.8.1 Primary endpoint(s)

The sample size was calculated for the two primary efficacy variables with adjustment for multiple testing by using the Bonferroni procedure.

For primary efficacy variable 1, i.e., percent change from baseline in LDL-C, the standard deviation is assumed to be 40, partly based on the results from ORION-10 and ORION-11 clinical trials, and considering that the standard deviation will likely be larger in this trial since changes in lipid-lowering therapy are allowed in both treatment groups. An expected mean treatment difference of 15 is assumed, which is smaller than the mean difference observed in the Phase III trials, to account for 1) potential lower utilization of background lipid-lowering therapy in the "inclisiran first" implementation group compared to the usual care group, and 2) the ability to add non-statin lipid lowering therapy (including participants who may have used commercially available inclisiran), in the usual care group.

Table 12-1 considers total sample sizes for expected mean treatment differences of 15, 20, and 25 and powers of 0.85 and 0.90 (nQuery Version 8.4.1.0). From Table 12-1, an expected mean treatment difference of 15 at Day 330 and a power of 0.90 were chosen to provide a total sample size of 354 participants.

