2.1 Data analysis general information

It is planned that the data from all centers that participate in this protocol will be combined, so that an adequate number of participants will be available for analysis.

Any data analysis carried out independently by the investigator should be submitted to Novartis before publication or presentation.

The analysis will be performed at the end of the trial, after the data for all participants are available.

Unless otherwise specified, all statistical tests will be conducted against a two-sided alternative hypothesis, employing a significance level of 0.05.

Efficacy, safety, and other data will be summarized. For continuous variables, summary statistics (mean, standard deviation, median, 25th and 75th percentiles, minimum, and maximum) at each time point and for change from baseline to each time point will be reported by treatment group. For discrete variables, frequency counts and percentages at each time point will be reported by treatment group.

Lipid Parameters Units

All tabular summaries, listings, and figures of lipid parameters will be provided in traditional units). All other laboratory parameters will be analyzed in SI units. Both traditional and SI units will be included in SDTM and ADaM datasets. The lipid parameters include the following:

1. LDL Cholesterol (mg/dL)
2. Total Cholesterol (mg/dL)
3. HDL Cholesterol (mg/dL)
4. Non-HDL Cholesterol (mg/dL)
5. VLDL Cholesterol (mg/dL)

6. Triglycerides (mg/dL)
7. Apolipoprotein B (mg/dL)
8. Lipoprotein(a) (mg/dL)

[REDACTED]

[REDACTED]

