2.5.2 Statistical hypothesis, model, and method of analysis

Primary efficacy variable 1

The null hypothesis is that the mean percent change from baseline in LDL-C at Day 330 for "inclisiran first" implementation strategy and usual care groups are equal. The alternative hypothesis is that the mean percent change from baseline in LDL-C at Day 330 for "inclisiran first" implementation strategy group is not equal to that of the usual care group.

Primary efficacy variable 1 will be analyzed using mixed-effects model repeated measures (MMRM) with treatment, visit (Day 90, Day 180, Day 270, Day 330), baseline, [REDACTED], [REDACTED], treatment-by-visit interaction, and baseline-by-visit interaction as explanatory variables. An unstructured covariance matrix will be assumed for this model. Least-squares mean of each treatment group, least-squares mean treatment difference, two-sided 97.5% confidence intervals for the treatments, two-sided 97.5% confidence interval for the treatment difference, and p-value based on the fitted MMRM will be reported for each applicable visit (day). If the p-value based on a two-sided test for treatment effect at Day 330 is < 0.025 and the corresponding least squares mean treatment difference ("inclisiran first" implementation strategy – usual care) is less than 0, statistical significance in favor of "inclisiran first" implementation strategy is shown. All efforts will be made to follow up participants until the end of the study. Participants will be expected to follow the visit schedule and assessments even after discontinuation of study treatment. Data after participants discontinued study treatment will be used in the analysis ("retrieved dropout").

The primary analysis of primary efficacy variable 1 will be based on the FAS. The primary analysis of this variable will be repeated for the Per-Protocol Set, Restricted Set 1, and Restricted Set 2.

Primary efficacy variable 2

The null hypothesis is that the difference ("inclisiran first" implementation strategy – usual care) in the proportion of participants who discontinue statin therapy at Day 330 is at least 0.15 (non-inferiority margin). The alternative hypothesis is that the difference ("inclisiran first" implementation strategy – usual care) in the proportion of participants who discontinue statin therapy at Day 330 is less than 0.15.

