For primary efficacy variable 2, a one-sided 98.75% confidence interval for treatment difference ("inclisiran first" implementation strategy – usual care) in the proportion of participants who discontinued statin therapy at Day 330 will be computed using the normal approximation to the binomial distribution. Non-inferiority of the "inclisiran first" implementation strategy to usual care will be declared if the upper limit of the confidence interval does not exceed the non-inferiority margin of 0.15. The difference in proportions and associated two-sided 97.5% confidence interval will also be provided.

The primary analysis of primary efficacy variable 2 will be based on the FAS excluding participants who had medical history of statin intolerance. The primary analysis of this variable will be repeated for the Per-Protocol Set and Restricted Set 2.

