For primary efficacy variable 2, i.e., discontinuation of statin therapy (yes, no), a z-test for a non-inferiority test of two proportions, an allocation ratio of 1:1, and a one-sided significance level of 0.0125 were used in the calculation of sample size. Table 3-2 considers total sample sizes for 0.20 and 0.25 as the true proportions of participants who discontinue statin therapy in each treatment group, and non-inferiority margins of 0.10 and 0.15 for the "inclisiran first" implementation group to be no worse than the usual care group (nQuery Version 8.4.1.0). From Table 3-2, a true proportion of 0.20 for participants who discontinue statin therapy in each treatment group by Day 330, a non-inferiority margin of 0.15, and a power of 0.90 were chosen to provide a total sample size of 354 participants.

Table 3-2 Sample Size Calculations for Statin Statin Therapy Discontinuation

Proportion in usual care group	Non-inferiority margin	Power = 0.85	Power = 0.90
0.20	0.10	688	796
0.20	0.15	306	354
0.25	0.10	806	932
0.25	0.15	360	414

Based on the sample size calculations in Table 3-1 and Table 3-2, a total sample size of 354 together with a loss to follow-up rate of 10% at Day 330 and a statin intolerance rate at baseline of 10% (i.e., a total of 20% due to loss to follow-up and statin intolerance at baseline) require

approximately 444 participants (222 participants per treatment group) to be randomized. This will also allow examination of subgroups with reasonable sample sizes.

4 Change to protocol specified analyses

Changes from Protocol version 01 (amended protocol) include the following:

1. Protocol Section 12.4.2 states that an unstructured working correlation matrix will be assumed for the MMRM. An unstructured covariance matrix will be used instead.
2. The protocol uses Day 0 as the first inclisiran dose day. In order to aid in counting of dosing days the first dose day will be referred to as Day 1.

Changes from Protocol version 02 (amended protocol) include the following:

3. Protocol Section 12 notes that the interquartile range will be provided. In order to streamline the tables this statistic was removed.
4. Protocol Section 12.2 notes that relevant medical histories and current medical conditions at baseline would be summarized using the Safety Set, the FAS was used instead.

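### Optional gain, not an error: the two primary tests keep fixed Bonferroni levels after one succeeds; Holm would hold the same familywise bound and add about 3 to 4 points of power to each claim on the planning inputs

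*Protocol*

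**What the plan says.** Protocol 12.4.2 gives two declaration rules, neither of which refers to the other.

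- **LDL-C:** success if the "p-value based on a two-sided test for treatment effect at Day 330 is" below 0.025 and the least-squares mean difference is negative. SAP 2.5.2 repeats this ("two-sided test for treatment effect at Day 330 is < 0.025").
- **Statin discontinuation:** both documents use "a one-sided 98.75% confidence interval for treatment difference", and non-inferiority "will be declared if the upper limit of the confidence interval does not exceed the non-inferiority margin of 0.15". SAP 2.5.2 adds: "The difference in proportions and associated two-sided 97.5% confidence interval will also be provided". The upper end of that interval is the same 98.75% limit.

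Protocol 12.8.1 and SAP Section 3 base the sample size on "adjustment for multiple testing by using the Bonferroni procedure". As a general default, SAP 2.1 says that, unless otherwise specified, "all statistical tests will be conducted against a two-sided alternative hypothesis, employing a significance level of 0.05"; Protocol Section 12 says the same.

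No visible text in either document sets a testing order, a fallback, or a transfer of alpha after one success. SAP Section 4, including the items under "Changes from Protocol version 02 (amended protocol) include the following", adds none. The two documents agree with each other.

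**The concern.** Fixed Bonferroni holds each claim to half of the implied overall level even after the other has succeeded, when the familywise bound no longer requires it. A true second claim could be missed for that reason alone. Protocol 1.2 gives the purpose of the trial as LDL-C reduction and statin discontinuation together, so the chance of making both claims matters. The planned LDL-C difference of 15 was set below the Phase III difference (Protocol 12.8.1). If the true effect is larger than 15, nearly all of the available gain falls on statin non-inferiority.

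**Working it through.** **1. Inputs (Protocol 12.8.1, SAP Section 3).** LDL-C: difference 15, SD 40, two-sided 0.025. Non-inferiority: true rate 0.20 in each arm, margin 0.15, one-sided 0.0125. Power 0.90 for each; 1:1 allocation; 20% inflation in total (10% loss to follow-up plus 10% statin intolerance).

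**2. The plan's own figures.** With z(0.9875) = 2.2414 and z(0.90) = 1.2816, (2.2414 + 1.2816)² = 12.41.

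- LDL-C: n per arm = 2 × 40² / 15² × 12.41 = 14.22 × 12.41 = 176.5, so 177 (354 in total).
- Non-inferiority: n per arm = 2 × 0.20 × 0.80 / 0.15² × 12.41 = 14.22 × 12.41 = 176.5, so 177 (354 in total).
- Inflation: 177 / 0.80 = 221.25, so 222 per arm (444 in total).

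Every cell of Protocol Tables 12-1 and 12-2 reproduces. The split is built into the sample size: at unsplit alpha each total would be 300.

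**3. Why Holm keeps the bound.** In the favorable direction each test has one-sided level 0.0125. If both nulls are true, a first error must occur at step one, with probability at most 0.0125 + 0.0125 = 0.025. If only one null is true, it is never tested above 0.025. So the bound is 0.025 one-sided (0.05 two-sided) under any dependence. Holm rejects everything that Bonferroni rejects.

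**4. Power of each test.** LDL-C uses 222 × 0.90 = 199.8, or about 200 per arm (noncentral t); non-inferiority uses the planning 177 per arm (unpooled normal approximation).

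- LDL-C: 0.9328 at two-sided 0.025; 0.9625 at two-sided 0.05.
- Non-inferiority: SE = √(2 × 0.20 × 0.80 / 177) = 0.04252 and 0.15 / 0.04252 = 3.528. Φ(3.528 − 2.241) = 0.9008 at 0.0125; Φ(3.528 − 1.960) = 0.9415 at 0.025.

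**5. Bonferroni against Holm, independent tests.** Holm power for one test = power at the half level + (power at the full level − power at the half level) × the other test's power at its half level.

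| Claim | Bonferroni | Holm |
|---|---|---|
| LDL-C | 0.933 | 0.9328 + 0.0297 × 0.9008 = 0.960 |
| Non-inferiority | 0.901 | 0.9008 + 0.0407 × 0.9328 = 0.939 |
| Both | 0.9328 × 0.9008 = 0.840 | 0.905 |
| At least one | 1 − 0.0672 × 0.0992 = 0.993 | 0.993 |

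The documents give no correlation between the two statistics. Over an assumed range of −0.5 to 0.5, power for both claims goes from 0.834–0.858 (Bonferroni) to 0.904–0.912 (Holm). At an LDL-C difference of 20, LDL-C goes from 0.997 to 0.999 and non-inferiority from 0.901 to 0.941.

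**6. Under the SAP's handling of early terminators.** SAP 2.5.1 and 2.5.4 score early terminators as discontinued, so they stay in the analysis; SAP 2.5.2 removes only participants with a history of statin intolerance. On the planning rates this leaves 222 × 0.90 ≈ 200 per arm. Assume that the 10% lost all count as discontinued and 20% of the rest stop: 0.10 + 0.20 × 0.90 = 0.28. Then SE = √(2 × 0.28 × 0.72 / 200) = 0.0449 and 0.15 / 0.0449 = 3.341, giving 0.864 at 0.0125 and 0.916 at 0.025. Holm gives 0.864 + 0.052 × 0.933 = 0.913.

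**7. The price.** Suppose inclisiran-first is truly worse by the margin (0.35 against 0.20) and the LDL-C effect is as planned. False non-inferiority rises from 0.0125 to 0.0125 + 0.0125 × 0.9328 = 0.0242 (0.0212 to 0.0250 over the same correlations).

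The 98.75% limit can also exceed 0.15 when Holm declares non-inferiority. With 35 of 177 discontinuing in usual care:

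| Inclisiran-first, of 177 | 98.75% limit | 97.5% limit |
|---|---|---|
| 44 | 0.1499 | 0.1374 |
| 45 | 0.1559 | 0.1434 |
| 46 | 0.1620 | 0.1494 |
| 47 | 0.1680 | 0.1554 |

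So 44 passes now and 46 passes under Holm. The chance of such a declaration is 0.0407 × 0.9328 = 0.038, which is 0.038 / 0.939 = 4.0% of Holm's non-inferiority declarations.

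**The case against.** The strongest reply is that nothing needs repair. Protocol and SAP agree, the split is already paid for in the sample size, and the chance of at least one claim does not move. Changing a primary decision rule late in an open-label trial, where physicians see on-study LDL-C, invites a credibility challenge for a few points of power. The gain falls mainly on the non-inferiority claim, where caution is easiest to defend, and the actual false-claim rate there nearly doubles. Bonferroni intervals have joint coverage; step-down intervals do not. All of this stands. It is why the point is optional and why the costs belong in any amendment.

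Two further objections limit the claim. First, a reader might take the 0.05 in Protocol Section 12 and SAP 2.1 as a stated familywise level. It is a per-test default that applies unless otherwise specified, and the primary tests are otherwise specified. The familywise 0.05 is an inference from Bonferroni at 2 × 0.025. Second, a reader might infer that each test is assured its planned 90% power. That holds on the planning inputs only; step 6 gives 0.864 for non-inferiority under its assumptions. The counts out of 177 are likewise illustrative, because the SAP analysis would have a different denominator.

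The word co-primary in Protocol 4.1, SAP 1.1 and SAP 2.2.1 could suggest that both tests must succeed. No overall success rule is stated, but a both-must-win design needs no alpha split. The split and the separate declarations show either-or testing, which is where Holm applies.

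**Conclusion.** The concern holds as an inexpensive improvement. The current plan is valid. A reader might infer that error control fails or that the trial is underpowered against its stated target; the documents support neither, since the bound is respected and 354 and 444 reproduce.

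Holm adds 2.7 points for LDL-C, 3.8 for non-inferiority and 6.5 for both claims, assuming independence, 200 and 177 per arm, and the planning effects. Under the assumed 0.28 rate with 200 per arm, the non-inferiority gain is 4.9 points. These gains concern the second claim only. Whether they are worth a higher false non-inferiority rate, still within 0.025 one-sided, is for the sponsor to weigh. SAP v3.0 is marked as prior to database lock; the documents do not show whether lock or a between-arm comparison has since taken place.

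**What to change.** If the database is not locked and the arms have not been compared, amend Protocol 12.4.2 and SAP 2.5.2 as follows.

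1. Test both variables at the current levels.
2. If only LDL-C succeeds (p < 0.025 and difference < 0), retest non-inferiority with the one-sided 97.5% upper limit against 0.15.
3. If only non-inferiority succeeds, retest LDL-C at two-sided 0.05 with difference < 0.
4. If both succeed at the first step, the current intervals govern and no retest is needed.
5. Keep the 98.75% one-sided and 97.5% two-sided intervals as the reported simultaneous intervals. State that second-step intervals support the decision only and lack joint coverage.
6. State the implied familywise level explicitly, and replace co-primary with primary.

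The cost is a protocol amendment with the approvals in Protocol 14.1, a SAP update, and at most one extra interval per endpoint; no new data. The amendment should disclose the rise in false non-inferiority to about 0.024 when the LDL-C effect is real, and the roughly 4% of non-inferiority declarations in which the 98.75% limit would lie above 0.15. If the database is locked or the arms have been compared, leave the plan as it is.

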### 12.4.3 Handling of intercurrent events of primary estimand

The remaining intercurrent events of the primary estimand for the two primary efficacy variables are the following: 1. Potential use of inclisiran by participants in the usual care group. This intercurrent event will be ignored in the analysis, as the design of the trial allows for participants in the usual care group to potentially use inclisiran. 2. Discontinuation of study treatment. This intercurrent event will be ignored in the analysis.

### 12.4.4 Handling of missing values not related to intercurrent event

For the primary analysis of primary efficacy variable 1, the MMRM implicitly imputes missing data under a missing at random assumption.

For the primary analysis of primary efficacy variable 2, participants for whom it cannot be ascertained that they are on statin therapy at the end of study will be assumed to have discontinued statin therapy.

### 12.4.5 Sensitivity analyses

The sensitivity analysis of primary efficacy variable 1 to address the primary objective will be based on the following estimand:

- Population: Defined through appropriate inclusion/exclusion criteria to reflect the targeted population
- Variable: Percent change from baseline in LDL-C [The primary analysis time point is at Day 330.]
- Treatment: "Inclisiran first" implementation strategy or usual care
- Remaining intercurrent events: 1. Potential use of inclisiran by participants in the usual care group. This intercurrent event will be ignored in the analysis, as the design of the trial allows for participants in the usual care group to potentially use inclisiran. 2. Discontinuation of study treatment. This intercurrent event will be ignored in the analysis.
- Summary measure: Probability of observing the same or a more favorable response with "inclisiran first" implementation strategy relative to usual care

For the above estimand, primary efficacy variable 1 will be analyzed at each time point for the Full Analysis Set using the van Elteren test, adjusting for [REDACTED] (Stokes et al 2012). The probability of observing the same or a more favorable response with "inclisiran first" implementation strategy relative to usual care will be estimated using nonparametric methods, and the associated 97.5% confidence interval will also be reported (Chen and Kianifard 2000).

